8.5 Management of capecitabine administration

Patients will be instructed to take capecitabine tablets at a dose of 625mg/m² twice a day as per standard practice starting in the evening of day 1 of each cycle (stage A2 and B). For patients who find swallowing capecitabine difficult, it is possible to dissolve the tablets in lukewarm water. The capecitabine tablets should be placed in approximately 200ml of lukewarm water. By stirring for about 15 minutes the tablets should dissolve. There is no stability data for any form of capecitabine suspension, so this should be done immediately prior to use and the solution swallowed immediately, rinsing to ensure all of the contents are ingested. As the solution will have a bitter taste it could be flavoured with a fruit juice or squash, but grapefruit juice should not be used. The solution may also be administered through a naso-gastric tube or other enteral feeding tube. Please note that dissolving capecitabine is outside of its licensed indication.

In addition, it is recommended that patients are carefully monitored for ophthalmologic complications, such as keratitis and corneal disorders, especially if they have a prior history of eye disorders. Treatment of eye disorders should be initiated promptly. For patients with diabetes mellitus, caution must be exercised as it may be aggravated.

Concurrent chemoradiotherapy (Weeks 7-11)

Patients should be instructed to take the drug twice daily as above **only** on the days radiotherapy is delivered. Where the start of radiotherapy is delayed for scheduling reasons Day 1 of the third cycle of chemotherapy, i.e. Day 1 of the start of concurrent chemotherapy, should also be delayed such that the 2 treatments start together.

Additional dosing requirements are:

- Missed doses/dosing day will not be made up. The next dose must be taken as scheduled. The missed tablets should be brought at next clinic visit to be handed over to the research nurse.
- If a patient vomits after taking the tablets, they should not take another dose. The next doses should be taken as scheduled.
- Doses should NOT be doubled to make up for missed doses.
- Any unused tablets should be returned to pharmacy (via research nurse). All patients are asked to keep a record of their capecitabine use in their diary card.

8.6 Management of cisplatin administration

Cisplatin will be administered on day 1 of a 3 weekly cycle. From weeks 1 to 18 for Stage A2 and 1-11 for Stage B as an intravenous infusion at 60mg/m² over 2 hours on treatment days or as per local policy. The hydration regimen for cisplatin administration will be determined by locally agreed pharmacy procedures and guidelines. Pre and post anti-emetics should be given according to local practice for high risk emesis. Laboratory values required for administration of chemotherapy will be as per standard policy (for administration of M6620 (Berzosertib) see section 8.4). Patient monitoring and management of hypersensitivity and extravasation will be as per local hospital policy. Patients with significant hearing impairment will be made aware of potential ototoxicity. For those who choose to be included, it is recommended that audiograms be carried out at baseline and prior to cycle 2. Gastric protection (Proton Pump inhibitor or H2 blocker) is recommended for all patients for duration of therapy and for at least 6 weeks thereafter.

On days of concurrent chemo-radiation, cisplatin should be completed before radiotherapy treatment. Patients may undergo their radiotherapy during the post-hydration following cisplatin, which may be interrupted provided it is completed afterwards.

8.7 Managing delays to Chemotherapy and Radiotherapy

Where the start of radiotherapy is delayed for scheduling reasons Day 1 of the third cycle of chemotherapy, i.e. Day 1 of the start of concurrent chemotherapy, should also be delayed such that the 2 treatments start together. The decision as to the scheduling of chemotherapy as a result of delays to radiotherapy due to machine service days or breakdowns i.e. unscheduled interruptions to radiotherapy should be made at the clinical discretion of the local PI, although the first treatment of radiotherapy must be given on the same first day of cycle 3 of the chemotherapy schedule. Management of hypersensitivity and extravasation will be as per local hospital policy.

8.8 Laboratory values required for administration of chemotherapy

See table in section 8.4.

8.9 Calculating and recalculating doses

The dose of M6620 (Berzosertib) will be calculated for each patient based on actual weight. BSA will be calculated according to the DuBois and DuBois formula. The patient's weight should be recorded prior to every chemotherapy or chemoradiotherapy cycle to determine dose of chemotherapy. If a patient's weight changes by $\geq 10\%$ from baseline then drug doses should be recalculated. If a patient's weight changes by $<10\%$ the dose may be adjusted according to local policy/clinician's discretion, but is not an absolute requirement.

8.10 Chemotherapy Dose-banding

Dose banding will be permitted as per local hospital policy (assumes dose banding is within 5% of actual calculated dose). The Trials Office will request each site to state upfront whether or not dose banding will be used.

8.11 Dose capping

There will be no dose capping.

8.12 Compliance

Patients will be instructed to keep a record of compliance in terms of their capecitabine treatment, by means of using a study patient diary card provided to the patient by the site. Patients should be asked to bring completed diary cards or other records and all their unused / remaining capecitabine tablets (empty, open or unopened) with them to each clinic visit. Sites should count remaining capecitabine at each visit. The patient diary cards should not be sent to the Trial Office but kept by the centre to monitor patient drug compliance. Compliance of M6620 (Berzosertib) and Cisplatin will be monitored by the patient record.

Accountability logs are required for capecitabine to determine that patients have received at least 80% of the prescribed treatment dose. Returns should be reconciled against the patient diary and the reason for any discrepancy documented. Site staff will collect and count patient returns which must be recorded on the drug accountability log.

8.13 Management of overdose

Overdose of M6620 (Berzosertib) can result in an increase in the severity of M6620 (Berzosertib) toxicities (section 9.3.2). Medical management of overdose should include stopping the chemotherapeutic agents and customary therapeutic and supportive medical interventions aimed at correcting the presenting clinical manifestations and preventing their possible complications. An overdose of cisplatin or capecitabine should be managed as per standard policy.

9 TOXICITY MANAGEMENT

9.1 Dose Limiting Toxicity

9.1.1 Reporting a DLT

A dose limiting toxicity is a toxicity that is considered related to M6620 (Berzosertib) or the interaction between M6620 (Berzosertib) and radiotherapy or chemoradiotherapy. **Dose limiting toxicities should be reported within 24 hours of the site becoming aware using the SAE form and scan and email as a PDF attachment to [contact] and send an email notification to [contact].** For management of M6620 (Berzosertib) toxicities see section 9.3. Chemotherapy and radiotherapy toxicities should be managed as per standard practice.

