2.6 Recruitment Schematic

3 OBJECTIVES AND ENDPOINTS

3.1 Stage A

3.1.1 Stage A1

Primary Objective	Endpoints/ Outcome Measures	Time point(s) for evaluation of end point

 To determine the best tolerated M6620 (Berzosertib) treatment schedule (or phase II recommended dose (RPTD)) administered concomitantly with Radiotherapy only in the palliative treatment of oesophageal cancer 	Highest treatment schedule resulting in less than 25% dose limiting toxicity (DLT) rate (see section 9.1.2 for DLT definitions)	
 Week 9
Secondary Objectives	Endpoints/ Outcome Measures	

 To determine the safety and toxicity profile of M6620 (Berzosertib) administered concomitantly with RT only in the palliative treatment of oesophageal cancer 	
 Any toxicity grade ≥ 3 graded according to CTCAE v4.03 and length of time for toxicity to resolve 	
 During radiotherapy Weeks 1-3 Week 4, 9 and week 12

 To determine if M6620 (Berzosertib) can be delivered in combination with palliative RT 	
 Proportion of patients completing at least 75%, 90% and 100% of the planned RT dose 	
 End of radiotherapy End of Week 3

 Efficacy of the combination 	
 Objective tumour response (OR) as evaluated by CT scan and quantified by Response Criteria Evaluation (RECIST 1.1) PFS and OS from D1 In field radiotherapy control 	
 12 weeks 6 and 12 months
Tertiary Objectives	Endpoints/ Outcome Measures	

 Explore tumour characteristics associated with response 	
 Genotyping of tumours 	
 Pre-trial archival biopsy

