9.1.2 Definition of a DLT

Stage A1

DLTs will be defined as per NCI CTCAE v4.03 and include:

- Absolute neutrophil count (ANC) $<0.5 \times 10^9/L$ for >7 days
- Febrile neutropenia (fever of unknown origin without clinically or microbiologically documented infection) (ANC $<1.0 \times 10^9/L$, fever $\geq 38.5^\circ C$) lasting >3 days
- Infection (documented clinically or microbiologically) with Grade 3 or 4 neutropenia (absolute neutrophil count $<1.0 \times 10^9/L$)
- Platelets $<25 \times 10^9/L$
- Clinically significant bleeding attributed to grade 3 thrombocytopenia or requiring platelet transfusion
- Grade ≥ 3 oesophagitis onset within 2 weeks of starting radiotherapy
- Grade ≥ 3 pneumonitis onset within 3 months of starting radiotherapy
- Grade ≥ 3 nausea or vomiting not controlled by optimal outpatient anti-emetic treatment
- Grade ≥ 3 diarrhoea despite optimal outpatient anti-diarrhoeal medication use
- Other grade 3 \geq effects thought to be directly treatment related to the combination of M6620 (Berzosertib) with radiotherapy
- Any toxicity causing a delay of radiotherapy completion by greater than one week
- Missing 2 consecutive doses of M6620 (Berzosertib) within a cycle due to Grade ≥ 3 toxicity
- A delay of any of the 3 treatments of 7 days or more within a cycle due to treatment related toxicity
- An elevation of ALT or AST $>5 \times ULN$ lasting 8 days or more
- A concurrent elevation of ALT or AST $>3 \times ULN$ and total bilirubin $>2 \times ULN$ in whom there is no evidence of biliary obstruction or other causes that can reasonably explain the concurrent elevation
- Death due to drug related complications
- Cardiac:
 - QTc prolongation (any QTc interval ≥ 500 msec or any change in QTc interval ≥ 60 msec from baseline) on ECG, unless related to an electrolyte abnormality and prolongation resolves with correction of electrolyte abnormality

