 - Any of the following (CTCAE criteria): Grade 2 or greater ventricular arrhythmia (second or third degree AV block), severe sustained/symptomatic sinus bradycardia less than 45 beats per minute (bpm) or sinus tachycardia >120 bpm not due to other causes (e.g., fever), persistent supraventricular arrhythmia (e.g., uncontrolled/new atrial fibrillation, flutter, atrioventricular nodal tachycardia, etc.) lasting more than 24 hours, ventricular tachycardia defined as >9 beats in a row or any length of torsades de pointes (polymorphic ventricular tachycardia with long QTc), or unexplained recurrent syncope
 - Symptoms suggestive of congestive heart failure with confirmed Ejection Fraction (EF) $<40\%$ (by 2D-echocardiogram or Multiple Gated Acquisition [MUGA] scan)
 - Troponin T: level which is consistent with myocardial infarction

Stage A2

DLTs will be defined as per NCI CTCAE v4.03 and include:

- Absolute neutrophil count (ANC) $<0.5 \times 10^9/L$ for >7 days
- Febrile neutropenia (fever of unknown origin without clinically or microbiologically documented infection) (ANC $<1.0 \times 10^9/L$, fever $\geq 38.5^\circ C$) lasting >3 days

- Infection (documented clinically or microbiologically) with Grade 3 or 4 neutropenia (absolute neutrophil count $<1.0 \times 10^9/L$)
- Platelets $<25 \times 10^9/L$
- Clinically significant bleeding attributed to grade 3 thrombocytopenia or requiring platelet transfusion
- Grade ≥ 3 nausea or vomiting not controlled by optimal outpatient anti-emetic treatment
- Grade ≥ 3 diarrhoea despite optimal outpatient anti-diarrhoeal medication use
- Other grade ≥ 3 effects thought to be directly treatment related to the combination of M6620 (Berzosertib) with chemotherapy
- Missing 2 consecutive doses of M6620 (Berzosertib) within a cycle due to Grade ≥ 3 toxicity
- A delay of any of the 3 treatments of 7 days or more within a cycle due to treatment related toxicity
- An elevation of ALT or AST $>5 \times ULN$ lasting 8 days or more
- A concurrent elevation of ALT or AST $>3 \times ULN$ and total bilirubin $>2 \times ULN$ in whom there is no evidence of biliary obstruction or other causes that can reasonably explain the concurrent elevation
- Death due to drug related complications
- Cardiac:
 - QTc prolongation (any QTc interval ≥ 500 msec or any change in QTc interval ≥ 60 msec from baseline) on ECG, unless related to an electrolyte abnormality and prolongation resolves with correction of electrolyte abnormality

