9.2 Management of treatment toxicities

In response to a toxicity of unknown or indeterminate causality M6620 (Berzosertib) treatment should be primarily withheld followed by chemotherapy. In the case of M6620 (Berzosertib) or chemotherapy toxicity or dose modification during the concurrent chemoradiotherapy phase patients should continue with RT where possible. The decision as to whether to continue radiotherapy is at the discretion of the treating clinician. If toxicity could be attributable to systemic therapy or radiotherapy, systemic therapy should be withheld first (see section 12.8 for management of radiotherapy toxicities).

Appropriate dose modifications should be considered for all agents if grade 3 or 4 toxicity occurs (see section 9.3 and 9.4 below). In stage A2 dose reductions should not be made beyond 50% of starting dose and the patient should come off study if further Grade 3 or 4 non-haematologic toxicity or Grade 4 haematologic toxicity is then experienced.

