9.3 Management of M6620 (Berzosertib) drug toxicities

No dose modifications of M6620 (Berzosertib) may be made (see 9.3.1 for exception in stage A2 below). Treatment may be interrupted because of a non-DLT of Grade 3 or higher, at the discretion of the Investigator. Treatment may be resumed when all toxicities have returned to grade 2 or less, at the discretion of the Investigator. If two consecutive doses of M6620 (Berzosertib) within a cycle are missed due to M6620 (Berzosertib) related Grade ≥ 3 toxicity, this constitutes a DLT, and no further M6620 (Berzosertib) will be administered. Missed doses due to \leq Grade 2 events, will be classified as non-compliance, not a DLT. A delay of any of the 3 treatments of 7 days or more within a cycle due to treatment related toxicity would be considered a DLT.

If the subject misses a dose of M6620 (Berzosertib) for any reason other than toxicity the dose should not be made up and the scheduling should continue as normal, from the next planned dose of M6620 (Berzosertib), unless it is a Tuesday dose which can be made up on the following day (Wednesday). If radiotherapy is withheld for toxicity or other reasons, M6620 (Berzosertib) should also be withheld and the dosing schedule should continue from the next planned dose once radiotherapy has resumed (see also section 8.4).

In Stage A2, if a patient experiences a DLT, they may continue on trial treatment at the next lowest dose level at the discretion of the treating investigator.

In Stage B, if a patient experiences a DLT, the TMG will convene to decide whether it is appropriate for the patient to continue receiving trial treatment, potentially at a reduced frequency of doses.

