12.8 Management of radiotherapy toxicity

Radiotherapy interruptions will usually not be necessary. However, if radiation is held for any reason, all systemic therapy must also be held, including M6620 (Berzosertib). Interruptions may be kept to a minimum by the use of ancillary therapy and vigorous nutritional support. Interruptions are permitted only on the basis of toxicity. However, if the RT interruptions are due to either technical reasons or due to bank holidays, the schedule should be made up to account for this either on a Saturday or at the end of the treatment.

Toxicity	Radiotherapy treatment interruption required:	Restart radiotherapy:
Oesophagitis	Grade 4; see management of symptoms below. Aim to limit interruption to 3 treatment days (fractions).	
Haematological toxicity		
Neutrophils	Stop RT treatment if neutrophils $<0.5 \times 10^9/L$ or	If levels recover to $0.5 \times 10^9/L$ (neutrophils) and $25 \times 10^9/L$ (platelets)
Platelets	platelet count $<25 \times 10^9/L$ and monitor every 48 hours. Note: systemic therapy should be interrupted initially as per local policy.	
Non-Haematological toxicity		
All toxicities	Grade 3: stop systemic treatment first and aggressive management should be pursued as per protocol, if no recovery to \leq grade 2 within 48h, consider withholding radiotherapy as follows:	
Vomiting	≥ 6 episodes of vomiting (\geq grade 3) lasting ≥ 3 days and unresponsive to antiemetics	Resolves to \leq grade 2
Diarrhoea	An increase from a patients usual bowel habit of ≥ 7 watery stools/day (\geq grade 3) and unresponsive to antidiarrhoeals	Resolves to \leq grade 2
Weight loss	Loss $\geq 10\%$ (\geq grade 2) of pre-treatment weight	
Other ¹	Grade 3: withhold radiotherapy and chemotherapy	Resolves to \leq grade 2

¹Rarely, non-treatment related or unexpected toxicities may require interruption of therapy at the discretion of the treating oncologist. Interruption of therapy may continue until the toxicity has regressed to \leq grade 2 to allow resumption of therapy; however, every effort should be made to limit treatment interruptions to 1-2 weeks

Oesophagitis

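### The event coded as y = 1 in the TiTE-CRM is defined inconsistently: on attribution, on missed doses, on the Stage A1 pneumonitis period and on the Stage B delay threshold

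*Protocol*

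**What the plan says.** The endpoint tables in Protocol section 3 and SAP 2.2 send the reader to one place for the event: "see section 9.1.2 for DLT definitions". SAP 3.1.1 (general description of the TiTE-CRM) codes y as 1 for toxicity and 0 otherwise, with no definition of its own. Other current text bears on what counts.

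- **Attribution.** Protocol 9.1.1: "A dose limiting toxicity is a toxicity that is considered related to M6620 (Berzosertib) or the interaction between M6620 (Berzosertib) and radiotherapy or chemoradiotherapy". The lists in 9.1.2 include "A delay of any of the 3 treatments of 7 days or more within a cycle due to treatment related toxicity", and 9.3 repeats that item. The introduction to 14.5 requires standard-treatment toxicities to be reported because the TiTE-CRM design assumes an expected frequency of those plus M6620-related toxicities.
- **Missed doses.** 9.1.2: "Missing 2 consecutive doses of M6620 (Berzosertib) within a cycle due to Grade" 3 or higher toxicity, with no causality condition; the row in 14.5 says the same. 9.3 counts two consecutive doses that "within a cycle are missed due to M6620 (Berzosertib) related Grade" 3 or higher toxicity.
- **Stage A1 pneumonitis.** 9.1.2 counts grade 3 or higher onset up to 3 months from the start of radiotherapy. Protocol 2.1 and SAP Table 1 set a 9-week window, the endpoint time point is week 9, and 5.4.1 excludes DLT assessment at week 12.
- **Stage B radiotherapy delay.** More than 3 consecutive fractions in 9.1.2; 3 or more in 14.5.

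**The concern.** A DLT coded 1 or 0 feeds the primary endpoint, the schedule recommended for each next patient, and the safety rule that stops a stage when the probability that the lowest schedule exceeds the target passes 0.95 (SAP 3.3). If the site, the trial office and the statistician each follow a different section, the same clinical course can enter the model with different values.

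The target levels and skeletons are also tied to a basis. A 25% rate of all treatment-related DLTs and a 25% rate of M6620-related DLTs are different targets, and the sections do not agree on which is meant.

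**Working it through.** **1. Reproducing the plan's own figures.** Inputs from SAP Table 1: p_k = s_k^exp(α), α ~ N(0, 1.158²); A1 skeleton 0.12, 0.15, 0.18, 0.20, 0.22, 0.25 with target 0.25; A2 skeleton 0.17, 0.20, 0.25, 0.30 with target 0.30. One thousand simulated trials per stage assumed true rates equal to the skeleton, DLT times uniform in the window, and accrual every 8 weeks (A1) or 3 weeks (A2). Mean sample size was 17.3 (95% interval 10 to 20) in A1 and 15.9 (11 to 20) in A2, against the stated 18 (10, 20) and 16 (11, 20). No stated figure is wrong; the defect is in the definition.

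**2. Effect of one event in the first cohort.** Three patients on schedule 1, all weights 1, r DLTs. The posterior is proportional to exp(−α²/(2 × 1.158²)) × p₁^r × (1 − p₁)^(3−r). The safety probability is P(p₁ > target) = P(α < ln[ln(target)/ln(s₁)]), with cut-offs −0.425 (A1) and −0.387 (A2). Numerical integration gives:

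| DLTs of 3 | A1 mean, schedule 1 | A1 P(>0.25) | A2 mean, schedule 1 | A2 P(>0.30) |
|---|---|---|---|---|
| 0 | 0.078 | 0.097 | 0.090 | 0.084 |
| 1 | 0.314 | 0.577 | 0.330 | 0.517 |
| 2 | 0.505 | 0.889 | 0.521 | 0.853 |
| 3 | 0.667 | 0.984 | 0.683 | 0.975 |

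With 0 of 3, schedule 2 has mean 0.093 (A1) or 0.104 (A2), so the model escalates. With 1 of 3, schedule 1 is already above target, so it stays. Between 2 and 3 of 3 the safety rule changes from not met to met.

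**3. Where missed doses diverge.** The two rules differ only when the grade 3 or higher toxicity is judged not related to M6620. Counting both dose days, missing two consecutive doses takes:

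- twice-weekly dosing (A1 days 2, 5, 9, 12 and so on; A2 Tuesday and Friday): gaps of 3 or 4 days, so a hold of 4 or 5 days, too short for the 7-day delay item;
- weekly dosing (A1 days 2, 9, 16; A2 Tuesdays): a gap of 7 days, so 8 days, which on that reading the delay item already counts if the toxicity is treatment related.

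The missed-dose conflict therefore bites mainly on A1 schedules 2, 3, 5 and 6 and A2 schedules 2 and 4. First cohorts are on weekly schedule 1, so the table in step 2 bears on attribution, not on missed doses.

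**4. Where attribution diverges.** Take an A1 patient delayed 7 days by a toxicity judged to come from radiotherapy alone. The delay item counts it; 9.1.1 does not. The size of the difference in basis can be sketched for A1. Protocol 2.1 gives 15–20% background grade 3/4 toxicity. Assuming independence, an M6620-only target of 25% implies an all-cause rate of 1 − 0.85 × 0.75 = 0.36 to 1 − 0.80 × 0.75 = 0.40. An all-cause target of 25% leaves 1 − 0.75/0.80 = 0.06 to 1 − 0.75/0.85 = 0.12 for M6620. Grade 3/4 toxicity is not the DLT definition, so these figures are illustrative only.

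**5. Pneumonitis.** Three months is about 91 days and the window is 63, so 91 − 63 = 28 days of calendar time lie outside it. In Stage B radiotherapy starts in week 7, so 3 months ends at about week 6 + 13 = 19, inside the 24-week window. This mismatch is confined to A1.

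**6. Stage B threshold.** A delay of exactly 3 consecutive fractions is a DLT in 14.5 and not in 9.1.2. No effect can be computed, because SAP v2.0 omits the Stage B model.

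**The case against.** The strongest reply is that 9.1.1 acts as a gate over the whole 9.1.2 list. On that reading 9.3 merely applies the gate to missed doses, and the unattributed items fall into line. Its silence on chemotherapy alone is then a drafting slip, since the A2 list names "effects thought to be directly treatment related to the combination of M6620 (Berzosertib) with chemotherapy". This is a fair reading, but no passage states it, and it does not fit the delay item or the 14.5 introduction.

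Several stronger readings are tempting and are not supported:

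- **That 14.5 contradicts 9.1.2 on attribution.** Its ticked DLT rows repeat the 9.1.2 attribution wording. Only its introduction clashes, and with 9.1.1.
- **That 9.2 generates the missed-dose conflict.** It says "In response to a toxicity of unknown or indeterminate causality M6620 (Berzosertib) treatment should be primarily withheld followed by chemotherapy". But 14.3 classes possibly related events as drug-related, so such a case would ordinarily count under both rules.
- **That late pneumonitis would be lost.** 14.7 requires any SAE considered related to a study drug to be reported whenever it occurs, and the A1 final analysis waits for at least 3 months of follow-up. The open question is only whether the case changes y.
- **That the one-event figures measure the harm done.** They describe how any small CRM reacts to one event.

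Safeguards may also exist out of view. SAP 3.2 refers to a Protocol Decision Point Plan, SAP 7.3 to a dedicated CRF for the model data, and the TMG may over-rule the model.

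**Conclusion.** Wrong as written, and worth fixing, with moderate confidence. The attribution and missed-dose conflicts are contradictory rules in current text and bear on A1 and A2 dose decisions. The A1 pneumonitis period is a narrower mismatch: the window, the time point and the visit schedule all point to 9 weeks, and only the list runs longer. The Stage B threshold is minor.

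The size is conditional. If one first-cohort event is coded differently, the model recommendation can change between escalating and staying, or the 0.95 rule can change between met and not met. This assumes SAP Table 1 and full weights. The documents give no basis for how often it would happen, and the Decision Point Plan and CRF, which were not supplied, may settle the coding. A reader might infer that the recommendations are unreliable or that patients would be mis-assigned; the documents do not show that. The ambiguity affects what the TMG is shown, not automatically what is given.

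**What to change.** - Reconcile Protocol 9.1.1, 9.1.2, 9.3 and the introduction to 14.5 to one attribution basis chosen by the sponsor, including the missed-dose and delay items. Refer to it in SAP 3.1.1.
- Confirm that the target levels and skeletons are on that basis.
- Reconcile the A1 pneumonitis period with the 9-week window, and state in the SAP whether a case after week 9 is entered as y = 1 in later decisions and in the final MTD.
- Reconcile the Stage B fraction threshold between 9.1.2 and 14.5 before Stage B opens.

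If the Decision Point Plan or CRF already fixes the coding, the protocol and SAP should be aligned with it. The cost is wording in both documents and a statistician's check, with simulations re-run only if the targets or skeletons prove to be on another basis. If late pneumonitis is to count, add a DLT item at the existing week-12 visit; that visit still falls about a week short of 3 months. Which basis, threshold and period apply is for the sponsor.
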